4.3 Multi-Dose Cohort Expansion Phase (Part 2)

Part 2 is a multi-dose expansion cohort with repeat administrations of MGD014 at 300 mcg/kg; see Study Part 2 Schema, **Figure 5**. Up to 6 patients will be enrolled in Part 2.

Participants previously enrolled in and having completed Part 1 may be considered for enrollment in Part 2, provided they continue to meet all eligibility criteria, did not experience any DLT in Part 1, and do not have any detectable ADA at the completion of Part 1.

In Part 2, additional optional assessments on the effects of MGD014 on HIV latent infection parameters include measurements of resting cell infection (frequency of persistent infection of resting CD4 T cells) by QVOA, SCA, and T-cell phenotype and functional properties.

Figure 5 Part 2: Dose Expansion Study Schema

(a) Screening, eligibility and optional baseline leukapheresis (b) optional leukapheresis post-treatment for frequency of persistent infection of resting CD4 T cells.

Abbreviations: ADA = anti-drug antibody; ART = antiretroviral therapy; leuk = leukapheresis; PK = pharmacokinetics; QVOA = quantitative viral outgrowth assay.

Step 1 Optional Baseline Leukapheresis: After obtaining the informed consent and confirmation that the participant qualifies for the study, the participant enrolls in the study. If the participant gives consent, an optional baseline leukapheresis is completed. The resting CD4 T cells obtained in the leukapheresis will determine the baseline frequency of resting CD4 T-cell infection. Additionally, baseline measurements at 2 independent, pre-MGD014 time points will determine baseline T-cell function and SCA levels. Note: if the frequency of resting CD4 T cell infection is ≤ 0.3 infected cells per million (IUPM), as measured by QVOA, a further decrease from this low frequency of infection cannot be definitively measured given the QVOA assay threshold and variance [51].

Step 2 Treatment phase: Eligible participants will continue their ART regimen and receive 3 infusions of MGD014 at the dose of 300 mcg/kg. Participants are monitored for 6 hours on site following their first infusion. Participants will be monitored for 4 hours on site following subsequent infusions. Clinical and laboratory parameters for safety, including clinical assessment

of cytokine release, will be assessed after each MGD014 infusion. PK and PD data will be collected, and serial blood draws will be obtained to assess the impact on T cell functional properties.

Step 3 Post-treatment Phase: This phase begins following the Day 28 MGD014 infusion and includes the 14 days between Day 28 and Day 42, with the first post-treatment study visit at Day 42. Step 3 is conducted over a 6-week period. During Step 3, if a baseline leukapheresis was performed, a second and final leukapheresis procedure is completed 2 weeks (+/- 2 weeks) following the final MGD014 infusion, for assessment of potential reduction in the frequency of resting CD4 T cell infection by QVOA. Plasma HIV-1 RNA as measured by SCA may be assessed. Serial blood draws will be obtained to determine PK and PD measures, and impact on T cell function.

4.4 Dose Limiting Toxicity

DLT will be defined based on drug-related AEs that occur during the DLT period following MGD014 administration. For Part 1, the DLT period is 2 weeks following the single MGD014 infusion. For Part 2, the DLT period is defined as the period from initial infusion of MGD014 through 2 weeks following the last IV MGD014 infusion.

The severity of all AEs will be graded according to the Division of AIDS Table for Grading the Severity of Adult and Pediatric Adverse Events, corrected Version 2.1, July 2017, which can be found on the DAIDS Regulatory Support Center Web site: <http://rsc.tech-res.com/clinical-research-sites/safety-reporting/daids-grading-tables>.

A DLT is any \geq Grade 2 drug-related AE, with the following exceptions, based on the medical judgement of PI (or designee) and medical monitor:

- Grade 2 laboratory abnormality that lasts <72 hours and is not otherwise associated with clinical complications.
- Grade 2 fatigue that lasts <7 days.

In general, for participants who experience an AE that meets criteria for a DLT, subsequent administration of the study drug to that participant should be held pending management and/or resolution of the event and assessment of attribution to the study drug.

In Part 1, if a given dose level is found to exceed the MTD, meaning that \geq 2 participants experience a DLT in a single dose cohort, Part 2 will proceed with the MTD (the dose preceding the dose level at which MTD was exceeded). If only 1 participant was enrolled at the prior dose level, an additional 3 participants will be enrolled at the prior dose level for evaluation of the MTD.

In Part 2, if \geq 2 participants experience the same DLT, subsequent administration of the study drug to any participant should be held pending review by the PI (or designee), sponsor, and independent Safety Monitoring Committee (SMC). If toxicity is unacceptable, the study will be discontinued.

All participants who discontinue study treatment or follow-up procedures should comply with end of study procedures. The sponsor or its designee must be notified about discontinuation within 24 hours of such an event.

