Whenever possible, diagnoses should be given when signs and symptoms are due to a common etiology (e.g. cough, runny nose, sneezing, sore throat, and head congestion should be reported as "upper respiratory infection"). All treatment measures that are required for AE management must be recorded in the source document. The intensity (severity) of AEs will be assessed and serious events will be determined by the definition provided in **Section 12.1.5** above.

Clinical Laboratory Changes: Safety laboratory assessments will be carried out locally at UNC and evaluated by the PI to ensure participant safety. The PI is responsible for reviewing the results of all laboratory tests as they become available.

- Laboratory values that fall outside of a clinically accepted reference range or values that differ significantly from previous values must be evaluated by the Investigator (or designee) for clinical significance. The Investigator (or designee) may repeat the laboratory test or request additional tests to verify the results of the original laboratory tests.
- If the Investigator determines the laboratory value is an abnormal change from baseline and is of clinical significance for that participant, it is considered an AE.
- Generally, Grade 1 and Grade 2 laboratory findings need not be reported as AEs unless deemed clinically significant by the Investigator.
- Consistent with the DAIDS designation of Grade 3 events as severe or medically significant and Grade 4 events as life-threatening, Grade 3 and Grade 4 laboratory findings should be reported as AEs or SAEs, as appropriate.
- The test result or finding should be reported as the AE. Such laboratory values should generally be recorded as "increased" or "decreased" (e.g., change from baseline potassium of 5.0 to 3.5 mEq/L =potassium decreased).

The sponsor has responsibility for appropriate reporting of AEs to the regulatory authorities. The sponsor will also report to the Investigator (or designee) all suspected unexpected serious adverse reactions (SUSARs). The Investigator (or designee) must report SUSARs to the UNC IRB, unless otherwise required and documented by the IRB.

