14.9 Cohort Analyses and Monitoring

As described in [Section 4.2.1](#), the decision to escalate doses from cohort to cohort will only occur based on consensus supporting escalation by PI (or designee) and the medical monitor. The medical monitor and the PI (or designee) will review aggregate safety data up through Day 14 from all dosed participants from the prior dose cohort.

An independent Safety Monitoring Committee (SMC) will receive monthly study progress and safety monitoring reports. Study feasibility and the achievement of study milestones will be assessed in these reports. Additionally, accrual, baseline characteristics, conduct of the study (including premature study discontinuations), any interruptions of ART, virologic failures, and all reported toxicities and events will be monitored during the study on a monthly basis. The

individual safety data will be reviewed monthly to assess relation of all reported toxicities and AEs to the study treatment. The monthly data will be shared with the SMC for review.

If at any time during the study, two or more participants experience a toxicity that is Grade 3 or higher and definitely, probably, or possibly related to study treatment (as judged by the protocol team), or two or more participants experience the same DLT that is Grade 2 or higher, then enrollment into the study will be temporarily suspended and the independent SMC will be asked to review all safety data; review the relation to study treatment of the event(s); and recommend how the study should proceed with respect to resuming enrollment and continuing study treatment.

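### Part 2 schedules no chemistry after the third infusion until Day 63, 21 days after the DLT window closes, and no HIV RNA test while infusions are being given

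*Protocol*

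**What the plan says.** Protocol Section 4.4 counts as a DLT any drug-related adverse event of Grade 2 or higher. The only laboratory exception is a "Grade 2 laboratory abnormality that lasts <72 hours and is not otherwise associated with clinical complications". For Part 2, "the DLT period is defined as the period from initial infusion of MGD014 through 2 weeks following the last IV MGD014 infusion". If two or more Part 2 participants have the same DLT, "subsequent administration of the study drug to any participant should be held pending review by the PI", the sponsor and the Safety Monitoring Committee (SMC).

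Section 14.9 adds two triggers for suspending enrollment and asking the SMC to review. One is not tied to the DLT window: "If at any time during the study, two or more participants experience a toxicity that is Grade 3 or higher" that is at least possibly related. The other depends on DLTs being recognized: "two or more participants experience the same DLT that is Grade 2 or higher".

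Section 4.3 says of Part 2 that "Clinical and laboratory parameters for safety, including clinical assessment" of cytokine release "will be assessed after each MGD014 infusion". It names no panel and sets no deadline.

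The Part 2 table in Appendix 1 gives the actual schedule:
- Chemistry: screening and Days 0, 14, 28, 63 and 77. Days 42 and 49 are blank.
- CBC: the same days, plus enrollment and Day 42. Footnote 22 limits those two to leukapheresis, which Section 9.10 makes optional.
- HIV-1 RNA: screening and Day 77 only.

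Section 9.11 and footnote 19 let infusion-day safety labs be drawn up to 7 days early, and 9.11 requires review before dosing. Section 5.3 stops a participant's infusions when HIV RNA exceeds 150 copies/mL on two consecutive determinations.

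**The concern.** Safety is the primary objective, and Part 2 is the only place where repeat dosing is studied. The pre-dose panels on Days 14 and 28 serve as follow-up for infusions 1 and 2. Infusion 3 has no next infusion, so nothing plays that role for it.

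A laboratory change that causes no symptoms can become a DLT only if someone measures it. If it arises after infusion 3, it may resolve unseen. It may also first appear on Day 63, when it can no longer be dated to the window. It would then be missing or late for the Section 4.4 hold and for the same-DLT trigger in Section 14.9.

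The HIV RNA point is secondary. The Section 5.3 rule needs two results and is useful only while infusions remain, yet the schedule supplies none in that period.

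**Working it through.** **Inputs** (Protocol Sections 4.3, 4.4, 9.3 and 9.11; Appendix 1, Part 2)
- Infusions on Days 0, 14 and 28. The DLT window ends 14 days after the last.
- Visit windows: ±1 day at Days 14, 28 and 42; ±3 days at Days 63 and 77.
- Infusion-day labs up to 7 days early; screening up to 56 days before Day 0.

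**The plan's own figure.** Window close = 28 + 14 = Day 42. This matches Section 4.3, which puts the first post-treatment visit there.

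**Infusion 3 to next scheduled chemistry**
- Nominal: 63 − 28 = 35 days
- Shortest: (63 − 3) − (28 + 1) = 31 days
- Longest: (63 + 3) − (28 − 1) = 39 days

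**Window close to that panel** (subtract 14): 21 days nominal, range 17 to 25.

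**Between the two scheduled panels either side of infusion 3**
- Day 28 panel drawn on the day: 35 days
- Drawn 7 days early: 35 + 7 = 42 days
- Maximum with visit windows: 39 + 7 = 46 days

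**Share of the 42-day window after its last scheduled panel**
- 14/42 = 33%, or (14 + 7)/42 = 50% if the Day 28 panel is drawn on Day 21

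**Scheduled panels between the last infusion and window close**
- Part 2 chemistry: 0
- Part 2 CBC: 0 without leukapheresis, 1 with it
- Part 1 chemistry and CBC: 2 each (Days 1 and 7 of a 14-day window)

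**Drug remaining from infusion 3.** Section 4.5 anticipates an 8-day half-life. Assuming simple exponential decline, the fraction left is 0.5^(14/8) = 30% at Day 42 and 0.5^(35/8) = 5% at Day 63. A change that tracks exposure could have gone by the first panel.

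**HIV RNA**
- Scheduled results from Day 0 to Day 28: 0. The rule needs 2.
- Oldest the last scheduled value can be at infusion 3: 56 + 28 + 1 = 85 days
- Longest gap between scheduled values: 56 + 77 + 3 = 136 days
- Section 5.1 accepts a routine-care result from up to 14 days before screening. If one is used, and the 56 days run from the screening visit, these become 99 and 150 days.
- The single copy assay cannot fill the gap, because Section 9.16 has it stored and shipped in batch.

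**The case against.** **The Part 1 comparison can be turned round.** Counting every post-dose chemistry panel inside each DLT window gives two in each part: Days 1 and 7 in Part 1, and the Day 14 and Day 28 pre-dose panels in Part 2. Part 1's last in-window panel is Day 7, so 7/14 = 50% of its window is also uncovered. That is fair: relative to window length, Part 2 is no worse. In days the tail is longer (14 to 21 against 7), and only Part 2 has an infusion with no in-window panel after it.

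**The exposed event is narrow.** Section 12.2.1 says: "Generally, Grade 1 and Grade 2 laboratory findings need not be reported as AEs unless deemed clinically significant by the Investigator". The event must also be judged drug-related, and Section 4.4 leaves the exceptions to medical judgment. The hold then needs the same DLT in at least two of up to six people. This stands as a limit on likelihood, which the documents do not allow to be estimated. But a judgment on clinical significance, or on the 72-hour exception, needs a result to judge.

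**The consequence is limited.** Part 2 DLTs do not set the dose, and the affected participant has finished dosing. A late finding affects dosing only if others are still being treated, and the Part 2 accrual pace is not stated. A Day 63 result can still trigger the Grade 3 rule, and the SMC receives monthly reports. All of this stands. It limits the effect on dosing, not the gap in the safety data.

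**Other checks exist.** Footnote 18 provides contact 2 to 3 days after the Day 28 infusion. Day 42 has vital signs, a directed examination and adverse event review for everyone. Cytokines and T-cell phenotype are sampled 4 hours after infusion 3, so Section 4.3 is partly met. The investigator can order extra tests. None of these is scheduled safety chemistry or an all-participant CBC. Six weekly doses of up to 10 mg/kg in monkeys showed no clinical pathology effect, which is reassuring, but Section 2.2.2 notes that those animals lack the HIV target.

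**The viral-load rule is generic.** Section 5.3 covers both parts, and Part 1 has one infusion. Unscheduled or outside-care tests could still trigger it. Participants are below 50 copies/mL at screening and adherence is reviewed at every visit. This point is rightly ranked second.

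**Conclusion.** The point holds. No scheduled chemistry, and no CBC for those without leukapheresis, falls between infusion 3 and the close of the DLT window. The first chemistry comes 35 days after the infusion (31 to 39) and 21 days after the window closes (17 to 25). The schedule falls short of the intent of Section 4.3 rather than contradicting it.

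The practical exposure is mainly persistent silent Grade 2 changes and late recognition of higher grades. It is worth fixing because it concerns the primary objective and the remedy is small. The HIV RNA gap is real but carries less risk: the protocol has a stopping rule that its scheduled tests cannot trigger before any infusion.

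The conclusion rests on reading Appendix 1 by column position and on scheduled tests only.

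**What to change.** Amend the Part 2 table in Appendix 1.

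1. **Main change.** At the existing Day 42 visit, add chemistry and a safety CBC for all participants. With visit windows this falls (42 − 1) − (28 + 1) = 12 to (42 + 1) − (28 − 1) = 16 days after infusion 3, so at most 2 days past the window's end, and nominally 21 days sooner than now. A Grade 2 result would need a repeat to judge the 72-hour exception; Section 12.2.1 already allows repeats. One panel at this point will still miss changes that resolve earlier.
2. **Secondary change.** Add HIV-1 RNA to the Day 0 and Day 14 draws, with results reviewed before the Day 28 infusion. A Day 14 value of 50 copies/mL or more starts the Section 9.11 repeat at 1 to 4 weeks; if it exceeds 150, draw the repeat before Day 28. Those two visits are (28 − 1) − (14 + 1) = 12 to (28 + 1) − (14 − 1) = 16 days apart. Assay turnaround is not given, so the site must confirm that both results fit. No Day 42 test is needed, because no infusion remains to stop.

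**Cost.** One amendment to Appendix 1. The main change is at most 6 × 2 = 12 assays; both together are at most 6 × (1 + 1 + 2) = 24. No new scheduled visit is needed: Day 42 already has a PK draw for everyone, and Days 0 and 14 already have safety labs. The downsides are extra tubes, an unscheduled repeat draw if a Day 14 value exceeds 150, and possible repeat and resistance testing for transient blips. Even then the viral-load rule could stop only infusion 3. Sections 4.4, 5.3 and 14.9 and the SAP can stay as they are.

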Step 2 Treatment Phase: In the MGD014 treatment phase (infusion of DART® molecule), participants continue to take their ART and receive 1 infusion of MGD014 at a given dose level based on their assigned dose cohort. The first participants of each dose cohort are monitored for 24 hours on site following infusion; subsequent participants at the same dose level will be monitored for 12 hours on site following infusion. A minimum of 24 hours is required between each participant infusion in a dose cohort. Assessment of clinical and laboratory parameters for safety, including cytokine release, occurs after the MGD014 infusion. PK, PD, and RO data are also collected after the MGD014 infusion. A 2-week DLT period follows each dose cohort and the decision to escalate to the next dose cohort level depends on the results of the testing done during this period. Reference the study schema for Part 1 in [Figure 4](#).

Step 3 Post-treatment Phase: Participants progress to Step 3 two (2) weeks after completion of their infusion. This phase is 4 weeks in length and continues monitoring each participant for safety. Serial blood samples collected during this time will analyze the PK, PD and RO measures, and the impact on T-cell phenotype.

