- b. If any of the 3 additional participants experiences a DLT (so in total ≥ 2 of the participants experience a DLT within the same dose cohort), no further participants will receive a dose at this dose level, as the maximum tolerated dose (MTD) will have been exceeded. Part 2 will proceed with the MTD (the dose preceding the dose level at which MTD was exceeded). If only 1 participant was enrolled at the prior dose level, an additional 3 participants will be enrolled at the prior dose level for evaluation of the MTD.

[figure not shown]

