5.3 Guidelines for Discontinuation of Participants from Study Drug Administration

Under certain circumstances, an individual participant's infusions will be prematurely or permanently discontinued. Specific events that will result in stopping a participant's infusion schedule in either Part 1 or Part 2 of the study include:

- Failure to meet requirements established for safety assessment
- Pregnancy
- Development of a DLT at any time following MGD014 infusion
- Investigator discretion
- HIV RNA > 150 copies/mL on 2 consecutive determinations

If the PI (or designee) decides that a participant should be withdrawn from study treatment, the sponsor must be alerted within 24 hours. All participants who discontinue treatments should comply with protocol specified visits and follow-up as required by the protocol. The only exception to this requirement is when a participant withdraws consent for all study procedures or loses the ability to consent freely (i.e., is imprisoned or involuntarily incarcerated for the treatment of either a psychiatric or physical illness).

If a participant is withdrawn before completing the study, the reason for withdrawal must be documented appropriately in the study documents.

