12.2.2 Immediately Reportable Events

IREs are AEs that must be reported immediately to MacroGenics within 24 hours of the study site's awareness of the event:

- All SAEs
- Pregnancy in a study participant or partner of a study participant.
- The following AESI: \geq Grade 2 CRS /IRR
- Administration of a dose significantly greater (specifically, + 20 % or higher) than the planned dose, and results in an event of clinical consequence.
- AEs leading to permanent discontinuation of study drug in an individual participant.
- Withdrawal of the participant from study drug administration for any reason
- Product quality issues with an associated clinical consequence.
- Participant diagnosed with COVID-19/SARS-CoV-2 infection.

In those cases, in which the IRE is considered related to study drug, the study drug may be discontinued, and the participant will continue participation in the study for observational safety and analysis (except for cases where the participant is withdrawn from the study by the PI (or designee) or withdrew the consent). At any time after completion of the study, if an PI (or designee) becomes aware of a SAE that s/he suspects is related to study drug, the PI (or designee) should report the event to MacroGenics Product Safety.

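### In Part 2, two participants with different DLTs do not expressly pause dosing for the others, although any two DLTs in a Part 1 cohort would stop that dose level

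*Protocol*

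**What the plan says.** **Part 2.** Section 4.3 states: "Up to 6 patients will be enrolled in Part 2". Each person receives 300 mcg/kg on Days 0, 14 and 28. Section 4.4 sets the hold on all dosing: if two or more "participants experience the same DLT, subsequent administration of the study drug to any participant should be held pending review" by the PI, sponsor and SMC.

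**After a single DLT.** Section 4.4 says that "subsequent administration of the study drug to that participant should be held pending management and/or resolution of the event". Section 5.3 goes further and lists "Development of a DLT at any time following MGD014 infusion" among the events that stop a participant's infusions in either part. Section 12.2.2 makes "Withdrawal of the participant from study drug administration for any reason" reportable to the sponsor within 24 hours.

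**Any time in the study.** Section 14.9 suspends enrollment and calls for SMC review in two situations: two or more participants with a related Grade 3+ toxicity of any kind, or two or more with the same DLT of Grade 2 or higher. The SMC then advises on resuming enrollment and on continuing treatment. Otherwise the SMC receives monthly reports.

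**Part 1.** Section 4.4 counts DLTs of any kind: if two or more "participants experience a DLT in a single dose cohort, Part 2 will proceed with the MTD", meaning the preceding dose. Section 4.2.1 (Scenario 3b) adds that "no further participants will receive a dose at this dose level, as the maximum tolerated dose (MTD) will have been exceeded". Cohort 8 of Part 1 was 300 mcg/kg, the Part 2 dose.

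The SAP adds no hold or stopping rule for Part 2.

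**The concern.** The DLT definition is the same in both parts, yet the study-wide response in Part 2 depends on whether the two events match. The protocol gives no reason for the restriction and does not say what makes two DLTs the same (preferred term, organ class or mechanism).

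Part 2 is the first planned repeat dosing in people. If two participants have different DLTs, the rest can go on receiving the same dose with no required pause. The monthly SMC report is not timed to prevent this, because a participant's three infusions span 28 days and can all fall between two reports.

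**Working it through.** **1. The plan's own figures.** The documents give no operating characteristics for the Part 2 rule, so only the sample size can be reproduced. Part 1: 2 × 1 + 6 × 3 = 20. Adding six in Part 2 gives 26. Both match protocol 14.1.

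**2. The rules side by side.**

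| Two Part 2 participants have | 4.4: all dosing held | 14.9: enrollment suspended, SMC review | Such a pair in one Part 1 cohort, within its 2-week window |
|---|---|---|---|
| the same DLT | yes | yes | dose level stops |
| different DLTs, both Grade 2 | no | no* | dose level stops |
| different DLTs, one Grade 2 and one Grade 3+ | no | no* | dose level stops |
| different DLTs, both Grade 3+ | no | yes, but doses not expressly held | dose level stops |

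*Section 14.9 is not limited to Part 2. An earlier related Grade 3+ event would complete the pair in the third row, and an earlier DLT of the same kind could complete one in either row.

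**3. Infusions at stake.** Planned: 6 × 3 = 18. If all six have had one infusion and two then have different DLTs, 4 × 2 = 8 infusions to the others are not expressly held. If only two people have been dosed and both have different Grade 2 DLTs, 4 × 3 = 12 infusions remain and enrollment is not suspended.

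**4. How often.** The documents give none of the following, so all are assumptions: DLT risk p per participant, k equally likely kinds, at most one DLT each, all independent. With M ~ Binomial(6, p),

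P(two or more DLTs, none alike) = Σ over m ≥ 2 of P(M = m) × k(k−1)…(k−m+1)/k^m.

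For k = 3 the second factor is 2/3 at m = 2, 2/9 at m = 3, and 0 beyond.

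- p = 0.10: 0.0984 × 2/3 + 0.0146 × 2/9 = 0.069
- p = 0.20: 0.2458 × 2/3 + 0.0819 × 2/9 = 0.182
- p = 1/3: 0.3292 × 2/3 + 0.2195 × 2/9 = 0.268

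| | p = 0.10 | p = 0.20 | p = 1/3 |
|---|---|---|---|
| Two or more DLTs of any kind | 0.114 | 0.345 | 0.649 |
| At least two alike (4.4 hold acts), k = 3 | 0.045 | 0.163 | 0.381 |
| None alike, k = 3 | 0.069 | 0.182 | 0.268 |
| None alike, k = 2 | 0.049 | 0.123 | 0.165 |
| None alike, k = 5 | 0.086 | 0.239 | 0.385 |
| None alike, three kinds weighted 70/15/15 | 0.047 | 0.122 | 0.174 |

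At p = 0.05 and k = 3, none alike is 0.021.

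**5. Neither 4.4 nor 14.9 acts.** Let g be the assumed share of DLTs that are Grade 3+. Multiply each term in step 4 by P(at most one Grade 3+) = (1−g)^m + m·g·(1−g)^(m−1). If Part 1 already had one related Grade 3+ event, use (1−g)^m instead. For k = 3:

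| | p = 0.10 | p = 0.20 | p = 1/3 |
|---|---|---|---|
| g = 0.25, no earlier Grade 3+ event | 0.064 | 0.169 | 0.247 |
| g = 0.50, no earlier Grade 3+ event | 0.051 | 0.132 | 0.189 |
| g = 0.25, one earlier event | 0.038 | 0.100 | 0.144 |
| g = 0.50, one earlier event | 0.017 | 0.043 | 0.061 |

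The documents do not say whether such an event occurred.

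**The case against.** The strongest defence is that Part 1 and Part 2 do different jobs. The Part 1 rule finds an MTD from events within 2 weeks of one dose. Part 2 expands a dose already selected, with a DLT window of about 6 weeks and three infusions, so a DLT after Day 14 would not have counted in Part 1. Since a DLT can be a Grade 2 event rated only possibly related, waiting for a repeated signal is a defensible policy. All of this stands. It rules out importing the Part 1 consequence, but not a pause for a review that 4.4 already provides for.

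Second, a reader might infer that two different DLTs go unanswered. The documents do not support that. Each affected participant is held or stopped, the withdrawal is reported within 24 hours, the PI and medical monitor judge what counts as a DLT, and safety data are reviewed monthly. The PI can also pause by discretion. Only an automatic study-wide pause is absent.

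Third, equally likely kinds works against a same-DLT rule. The protocol's main expected toxicity is infusion reaction or cytokine release, and if one kind dominates the percentages fall, as the 70/15/15 row shows. This stands.

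Fourth, it is tempting to add that Part 2 lacks the Part 1 spacing rule ("A minimum of 24 hours is required between each participant infusion in a dose cohort"). The readable Part 2 text states no interval, but Figure 5 and the infusion SOP cannot be seen. Spacing first infusions would also address single-dose exposure, already given at 300 mcg/kg in Cohort 8, and not repeat-dose risk. It is an optional preference and no part of this point.

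**Conclusion.** The concern holds as a gap in the Part 2 rules. Two different DLTs do not expressly hold the other participants' infusions at any grade. Unless both are Grade 3+, or an earlier event counts under 14.9, they also bring no SMC review beyond the monthly report.

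Under step 4's assumptions with three equal kinds, the gap arises in about 7%, 18% or 27% of trials at DLT risks of 10%, 20% or 33%. That is 60%, 53% or 41% of the trials with two or more DLTs. The figures in step 5 for no earlier event are upper bounds if Part 1 had a related Grade 3+ event. The direction depends only on more than one kind of DLT being possible; the sizes depend on the assumed risks and kinds.

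A reader might infer that 300 mcg/kg is unsafe. Nothing here supports that: section 2.4.3 reports no infusion reactions or cytokine release through Cohort 8, and the dose is 33-fold below the monkey NOAEL (2.4.2). This is a worthwhile, cheap correction to a safety rule, held with medium confidence.

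**What to change.** **Section 4.4, Part 2.** Replace the trigger with: *If two or more Part 2 participants have a DLT, of the same kind or not, all further MGD014 infusions will be held until the PI (or designee), the sponsor and the SMC have reviewed the events.*

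**Section 14.9.** For Part 2, change *the same DLT* to *a DLT*, and state that infusions for enrolled participants are also held while the SMC reviews.

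**Cost.** One sentence in 4.4, and a phrase and a clause in 14.9. With three equally likely kinds, the wider trigger adds a dosing hold in about 2%, 7%, 18% or 27% of trials at DLT risks of 5%, 10%, 20% or 33%, and fewer if one kind dominates. Some holds will be for Grade 2 events rated only possibly related. A hold may push a Day 14 or Day 28 infusion past its 1-day window, as the present hold also could.
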